APPENDIX 1 ECOG PERFORMANCE STATUS

| ECOG PERFORMANCE STATUS ^a | |
|--------------------------------------|---|
| 0 | Fully active, able to carry on all pre-disease performance without restriction |
| 1 | Restricted in physically strenuous activity but ambulatory and able to carry out work of a light or sedentary nature, eg, light house work, office work |
| 2 | Ambulatory and capable of all selfcare but unable to carry out any work activities. Up and about more than 50% of waking hours |
| 3 | Capable of only limited selfcare, confined to bed or chair more than 50% of waking hours |
| 4 | Completely disabled. Cannot carry on any selfcare. Totally confined to bed or chair |
| 5 | Dead |

^a Oken MM, Creech RH, Tormey DC, Horton J, Davis TE, McFadden ET, and Carbone PP. Toxicity and Response Criteria of the Eastern Cooperative Oncology Group. Am J Clin Oncol 1982; 5: 649-655.

APPENDIX 2 MANAGEMENT ALGORITHMS

These general guidelines constitute guidance to the Investigator and may be supplemented by discussions with the Medical Monitor representing the Sponsor. The guidance applies to all immuno-oncology agents and regimens.

A general principle is that differential diagnoses should be diligently evaluated according to standard medical practice. Non-inflammatory etiologies should be considered and appropriately treated.

[figure not shown]
Corticosteroids are a primary therapy for immuno-oncology drug-related adverse events. The oral equivalent of the recommended IV doses may be considered for ambulatory patients with low-grade toxicity. The lower bioavailability of oral corticosteroids should be taken into account when switching to the equivalent dose of oral corticosteroids.

Consultation with a medical or surgical specialist, especially prior to an invasive diagnostic or therapeutic procedure, is recommended.

The frequency and severity of the related adverse events covered by these algorithms will depend on the immuno-oncology agent or regimen being used.

GI Adverse Event Management Algorithm

Rule out non-inflammatory causes. If non-inflammatory cause is identified, treat accordingly and continue I-O therapy. Opiates/narcotics may mask symptoms of perforation. Infliximab should not be used in cases of perforation or sepsis.

[figure not shown]

Patients on IV steroids may be switched to an equivalent dose of oral corticosteroids (e.g. prednisone) at start of tapering or earlier, once sustained clinical improvement is observed. Lower bioavailability of oral corticosteroids should be taken into account when switching to the equivalent dose of oral corticosteroids.

Updated 05-Jul-2016

Renal Adverse Event Management Algorithm

Rule out non-inflammatory causes. If non-inflammatory cause, treat accordingly and continue I-O therapy

[figure not shown]

Patients on IV steroids may be switched to an equivalent dose of oral corticosteroids (e.g. prednisone) at start of tapering or earlier, once sustained clinical improvement is observed. Lower bioavailability of oral corticosteroids should be taken into account when switching to the equivalent dose of oral corticosteroids.

Updated 05-Jul-2016

Pulmonary Adverse Event Management Algorithm

Rule out non-inflammatory causes. If non-inflammatory cause, treat accordingly and continue I-O therapy. Evaluate with imaging and pulmonary consultation.

[figure not shown]

Patients on IV steroids may be switched to an equivalent dose of oral corticosteroids (e.g. prednisone) at start of tapering or earlier, once sustained clinical improvement is observed. Lower bioavailability of oral corticosteroids should be taken into account when switching to the equivalent dose of oral corticosteroids.

Updated 05-Jul-2016

Hepatic Adverse Event Management Algorithm

Rule out non-inflammatory causes. If non-inflammatory cause, treat accordingly and continue I-O therapy. Consider imaging for obstruction.

Patients on IV steroids may be switched to an equivalent dose of oral corticosteroids (e.g. prednisone) at start of tapering or earlier, once sustained clinical improvement is observed. Lower bioavailability of oral corticosteroids should be taken into account when switching to the equivalent dose of oral corticosteroids.

[figure not shown]
*I-O therapy may be delayed rather than discontinued if AST/ALT \leq 8 x ULN or T.bili \leq 5 x ULN.

**The recommended starting dose for grade 4 hepatitis is 2 mg/kg/day methylprednisolone IV.

Updated 05-Jul-2016

Endocrinopathy Management Algorithm

Rule out non-inflammatory causes. If non-inflammatory cause, treat accordingly and continue I-O therapy. Consider visual field testing, endocrinology consultation, and imaging.

[figure not shown]

Patients on IV steroids may be switched to an equivalent dose of oral corticosteroids (e.g. prednisone) at start of tapering or earlier, once sustained clinical improvement is observed. Lower bioavailability of oral corticosteroids should be taken into account when switching to the equivalent dose of oral corticosteroids.

Updated 05-Jul-2016

Skin Adverse Event Management Algorithm

Rule out non-inflammatory causes. If non-inflammatory cause, treat accordingly and continue I-O therapy.

Patients on IV steroids may be switched to an equivalent dose of oral corticosteroids (e.g. prednisone) at start of tapering or earlier, once sustained clinical improvement is observed. Lower bioavailability of oral corticosteroids should be taken into account when switching to the equivalent dose of oral corticosteroids.

[figure not shown]
*Refer to NCI CTCAE v4 for term-specific grading criteria.

^If SJS/TEN is suspected, withhold I-O therapy and refer patient for specialized care for assessment and treatment. If SJS or TEN is diagnosed, permanently discontinue I-O therapy.

Updated 05-Jul-2016

Neurological Adverse Event Management Algorithm

Rule out non-inflammatory causes. If non-inflammatory cause, treat accordingly and continue I-O therapy.

Patients on IV steroids may be switched to an equivalent dose of oral corticosteroids (e.g. prednisone) at start of tapering or earlier, once sustained clinical improvement is observed. Lower bioavailability of oral corticosteroids should be taken into account when switching to the equivalent dose of oral corticosteroids.

Updated 05-Jul-2016

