4.7.5 Criteria to Resume Dosing

Subjects may resume treatment with study drug when the drug-related AE(s) resolve(s) to Grade 1 or baseline, with the following exceptions:

- Subjects may resume treatment in the presence of Grade 2 fatigue.
- Subjects who have not experienced a Grade 3 drug-related skin AE may resume treatment in the presence of Grade 2 skin toxicity.
- For participants with Grade 2 AST, ALT and/or Total Bilirubin Abnormalities, dosing may resume when laboratory values return to baseline and management with corticosteroids, if needed, is complete.
- Drug-related pulmonary toxicity, diarrhea, or colitis must have resolved to baseline before treatment is resumed. Subjects with persistent Grade 1 pneumonitis after completion of a steroid taper over at least 1 month may be eligible for retreatment if discussed with and approved by the BMS Medical Monitor.
- Subjects who received systemic corticosteroids for management of any drug-related toxicity must be off corticosteroids or have tapered down to an equivalent dose of prednisone ≤ 10 mg/day.

- Drug-related endocrinopathies adequately controlled with only physiologic hormone replacement may resume treatment after consultation with the BMS Medical Monitor. Adrenal insufficiency requires discontinuation regardless of control with hormone replacement.
- Troponin elevations will require the participant to undergo a cardiac evaluation. Following this evaluation, determination of further treatment will be based on the discussion with the BMS medical monitor/designee.
- Dose delay of nivolumab, BMS-986016 and ipilimumab (Combo B), which results in treatment interruption of > 6 weeks requires treatment discontinuation, with exceptions as noted in Section 4.7.6.
- Dose delay of ipilimumab in Combo A, which results in treatment interruption of > 12 weeks requires treatment discontinuation, with exceptions as noted in Section 4.7.6.
- Ipilimumab may not be resumed sooner than 6 weeks (+/- 3 days) after the prior ipilimumab dose for Combo A.
- In general, subjects who meet criteria to resume ipilimumab will also have met criteria to resume nivolumab, so it should be feasible to synchronize dosing of both drugs when resuming ipilimumab. In order to facilitate this, the dosing days of nivolumab and ipilimumab may be adjusted within the permitted +/- 3 day window, as long as consecutive nivolumab doses are given at least 12 days apart.

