4.7.6 Discontinuation Criteria

Treatment with study drug should be permanently discontinued for the following:

- Any Grade 2 drug-related uveitis or eye pain or blurred vision that does not respond to topical therapy and does not improve to Grade 1 severity within the re-treatment period OR requires systemic treatment
- Any Grade 3 non-skin, drug-related adverse event lasting > 7 days or recurs, with the following exceptions for laboratory abnormalities, diarrhea, colitis, neurologic toxicity, drug-related uveitis, pneumonitis, bronchospasm, hypersensitivity reactions, myocarditis, infusion reactions, and endocrinopathies:

- Grade 3 drug-related diarrhea, colitis, neurologic toxicity, uveitis, pneumonitis, bronchospasm, myocarditis, hypersensitivity reaction, or infusion reaction of any duration requires discontinuation
- Grade 3 drug-related endocrinopathies, adequately controlled with only physiologic hormone replacement do not require discontinuation. Adrenal insufficiency requires discontinuation regardless of control with hormone replacement.
- Grade 3 drug-related laboratory abnormalities do not require treatment discontinuation except:
 - ◆ Grade 3 drug-related thrombocytopenia > 7 days or associated with bleeding requires discontinuation
 - ◆ Any drug-related liver function test (LFT) abnormality that meets the following criteria require discontinuation:
 - Grade ≥ 3 drug-related AST, ALT or Total Bilirubin requires discontinuation.
Note: * In most cases of Grade 3 AST or ALT elevation, study drug(s) will be permanently discontinued. If the investigator determines a possible favorable benefit/risk ratio that warrants continuation of study drug(s), a discussion between the investigator and the BMS Medical Monitor/designee must occur.
 - Concurrent AST or ALT $> 3 \times$ ULN and total bilirubin $> 2 \times$ ULN
- Any Grade 4 drug-related adverse event or laboratory abnormality (including but not limited to creatinine, AST, ALT, or Total Bilirubin), except for the following events, which do not require discontinuation:
 - Grade 4 neutropenia ≤ 7 days
 - Grade 4 lymphopenia or leukopenia or asymptomatic amylase or lipase
 - Isolated Grade 4 electrolyte imbalances/abnormalities that are not associated with clinical sequelae and are corrected with supplementation/appropriate management within 72 hours of their onset

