- medical/surgical admission other than to remedy ill health and planned prior to entry into the study. Appropriate documentation is required in these cases
- admission encountered for another life circumstance that carries no bearing on health status and requires no medical/surgical intervention (eg, lack of housing, economic inadequacy, caregiver respite, family circumstances, administrative reason).
- Admission for administration of anticancer therapy in the absence of any other SAEs (applies to oncology protocols)

6.1.1 *Serious Adverse Event Collection and Reporting*

Sections 5.6.1 and 5.6.2 in the Investigator Brochure (IB) represent the Reference Safety Information to determine expectedness of serious adverse events for expedited reporting. Following the subject's written consent to participate in the study, all SAEs, whether related or not related to study drug, must be collected, including those thought to be associated with protocol-specified procedures. All SAEs must be collected that occur during the screening period and within 100 days of the last dose of study drug. For participants assigned to treatment and never treated with study drug, SAEs should be collected for 30 days from the date of treatment assignment. If applicable, SAEs must be collected that relate to any later protocol-specified procedure (eg, a follow-up skin biopsy).

The investigator should report any SAE that occurs after these time periods and that is believed to be related to study drug or protocol-specified procedure.

An SAE report should be completed for any event where doubt exists regarding its seriousness.

If the investigator believes that an SAE is not related to study drug, but is potentially related to the conditions of the study (such as withdrawal of previous therapy or a complication of a study procedure), the relationship should be specified in the narrative section of the SAE Report Form.

SAEs, whether related or not related to study drug, and pregnancies must be reported to BMS (or designee) within 24 hours of awareness of the event. SAEs must be recorded on the SAE Report Form; pregnancies on a Pregnancy Surveillance Form (electronic or paper forms). The preferred method for SAE data reporting collection is through the eCRF. The paper SAE/pregnancy surveillance forms are only intended as a back-up option when the eCRF system is not functioning. In this case, the paper forms are to be transmitted via email or confirmed facsimile (fax) transmission to:

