6.6 Potential Drug Induced Liver Injury (DILI)

Wherever possible, timely confirmation of initial liver-related laboratory abnormalities should occur prior to the reporting of a potential DILI event. All occurrences of potential DILIs, meeting the defined criteria, must be reported as SAEs (see [Section 6.1.1](#) for reporting details).

Potential drug induced liver injury is defined as:

1. AT (ALT or AST) elevation > 3 times upper limit of normal (ULN)
AND
2. Total bilirubin > 2 times ULN, without initial findings of cholestasis (elevated serum alkaline phosphatase),
AND
3. No other immediately apparent possible causes of AT elevation and hyperbilirubinemia, including, but not limited to, viral hepatitis, pre-existing chronic or acute liver disease, or the administration of other drug(s) known to be hepatotoxic.

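### The Appendix 2 hepatic footnote, as printed, permits delaying I-O therapy in a liver pattern for which Protocol Section 4.7.6 requires permanent discontinuation

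*Protocol*

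**What the plan says.** **Appendix 2, Hepatic Adverse Event Management Algorithm.** The asterisked footnote reads "I-O therapy may be delayed rather than discontinued if AST/ALT" is no more than 8 x ULN or total bilirubin is no more than 5 x ULN. It carries no exclusion for combined elevation and no pointer to Section 4.7.6.

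**Section 4.7.6, Discontinuation Criteria.** Under the heading of permanent discontinuation, the liver rule is: "Any drug-related liver function test (LFT) abnormality that meets the following criteria require discontinuation". Two items follow.

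- The first is Grade 3 or higher drug-related AST, ALT or total bilirubin. A note is attached: "In most cases of Grade 3 AST or ALT elevation, study drug(s) will be permanently discontinued". If the investigator sees a favourable benefit/risk balance for continuing, a discussion with the Medical Monitor must take place.
- The second begins "Concurrent AST or ALT" and is met when AST or ALT is above 3 x ULN and total bilirubin is above 2 x ULN. No note or exception is attached to it.

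**Which text governs.** Section 3.5 lists the reasons for which subjects must stop treatment and refers drug-related adverse events to Section 4.7.6. Section 4.7.3 also sends Grade 3 or higher AST, ALT or total bilirubin to discontinuation. Appendix 2 describes itself as guidance to the investigator that Medical Monitor discussions may supplement. Section 4.7.2 offers the algorithms as an aid in managing events, hepatic ones included. No sentence in these sections says which text prevails if they differ.

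**The concern.** The footnote relaxes a stop instruction into a delay. Its limits reach well above the two thresholds that Section 4.7.6 treats as a permanent stop when crossed together. An investigator with the algorithm page in hand could delay dosing and later resume a drug that Section 4.7.6 says must not be given again.

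What is at stake is re-exposure after a pattern that Section 6.6 treats as a warning sign. That section defines potential drug-induced liver injury with the same aminotransferase threshold and "Total bilirubin > 2 times ULN, without initial findings of cholestasis (elevated serum alkaline phosphatase"), plus the absence of another apparent cause.

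Hepatic events are not rare with these regimens. Section 1.4.2.2 reports drug-related hepatic select adverse events in 29.0% of 407 pooled melanoma subjects who received the nivolumab 1 mg/kg plus ipilimumab 3 mg/kg induction also used in Combo B, most of them Grade 3-4. That figure shows exposure to liver toxicity. It does not say how often the combined pattern occurs, and the protocol gives no such frequency.

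**Working it through.** The plan has no figure to reproduce. The check compares two printed rules as inequalities. Let A be AST or ALT and B be total bilirubin, both in multiples of ULN.

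**Inputs**

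- Stop rule (Section 4.7.6, combined item): A > 3 and B > 2.
- Delay rule (Appendix 2 footnote), literal reading: A ≤ 8 or B ≤ 5.
- Delay rule, stricter reading in which both limits must hold: A ≤ 8 and B ≤ 5.

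**Overlap**

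- Stricter reading: 3 < A ≤ 8 together with 2 < B ≤ 5.
- Literal reading: every point with A > 3 and B > 2, except where A > 8 and B > 5 at the same time.

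**Examples**

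| A | B | Stop rule met | Delay allowed, stricter | Delay allowed, literal |
|---|---|---|---|---|
| 3 | 2 | no (neither threshold exceeded) | yes | yes |
| 5 | 3 | yes (5 > 3, 3 > 2) | yes (5 ≤ 8, 3 ≤ 5) | yes |
| 8 | 5 | yes | yes | yes |
| 7 | 6 | yes | no (6 > 5) | yes (7 ≤ 8) |
| 9 | 4 | yes | no (9 > 8) | yes (4 ≤ 5) |
| 9 | 6 | yes | no | no |

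The overlap exists on either reading, so it does not depend on how 'or' is understood.

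**Does another section remove it?**

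- The benefit/risk note in Section 4.7.6 is worded for Grade 3 AST or ALT elevation and sits under the first item. It does not extend to the combined item. Even where it applies it requires a Medical Monitor discussion, which the footnote does not mention.
- Section 4.7.5 has a general rule, "Subjects may resume treatment with study drug when the drug-related AE(s) resolve(s) to Grade 1 or baseline", and a liver rule confined to Grade 2: "For participants with Grade 2 AST, ALT and/or Total Bilirubin Abnormalities, dosing may resume when laboratory values return to baseline". Neither mentions the combined pattern.
- Section 6.6 gives a reporting duty and no dosing instruction.
- Sections 3.5 and 4.7.3 point to Section 4.7.6 as the controlling list, but neither refers to the footnote.

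The comparison uses only limits printed as multiples of ULN. The footnote is not compared with the Grade 3 item, because the protocol does not print the grade boundaries.

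**The case against.** The strongest reply has four parts.

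1. **The flow chart is missing from the text reviewed.** The footnote qualifies whichever box carries the asterisk, and that box cannot be seen. It could limit the footnote to isolated elevations or print the combined criterion itself. This stands. A missing figure is not a fault in the plan, and a conflict in the complete algorithm cannot be shown from this text.

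2. **The body text already settles the dosing decision.** Section 3.5 makes discontinuation mandatory and refers to Section 4.7.6, which names the pattern. Section 4.7.6 adds that if a criterion is met and attribution is unclear, all study drugs stop. Appendix 2 is general guidance, and its footnote says only that therapy may be delayed, so an investigator who stops complies with both texts. This largely stands and is why the point is minor. It does not remove the printed permission, and no sentence subordinates the footnote.

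3. **Section 4.7.5 needs no bar.** A reader might infer that it positively allows resumption after the combined pattern. The documents do not support that: a subject who meets a permanent-discontinuation criterion is not a delay case, so the resumption rules are not reached. They come into play only if the investigator has already followed the footnote instead of Section 4.7.6.

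4. **Reporting gives a safeguard.** Cases meeting the full Section 6.6 definition are handled as serious adverse events, which "must be reported to BMS (or designee) within 24 hours of awareness of the event". This stands as mitigation for those cases. It does not correct a dosing instruction, and it does not rest on Section 6.6 for cases with initial cholestasis or another apparent cause.

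**Conclusion.** The point holds as a minor safety harmonisation matter. As printed, the footnote permits delay in a region where Section 4.7.6 requires a permanent stop: at least A above 3 and up to 8 x ULN with B above 2 and up to 5 x ULN, and more on the literal 'or'.

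This rests on two assumptions: that the unseen flow chart does not restrict the footnote, and that the liver abnormality is drug-related, as Section 4.7.6 requires. Confidence is moderate because of the first.

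A reader might infer that the protocol has no effective stop rule for this pattern, or that subjects would be re-treated in practice. The documents support neither: Section 4.7.6 is explicit and governs, and no frequency is given for the pattern or for reliance on the footnote. The wording does not affect the objective response rate, the sample size or any planned analysis.

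**What to change.** First check the hepatic flow chart to see where the asterisk sits and whether the combined criterion is already printed there. If it is not, add to the footnote: *except where the Section 4.7.6 discontinuation criteria are met, including concurrent AST or ALT > 3 x ULN and total bilirubin > 2 x ULN; Section 4.7.6 prevails*. For Grade 3 AST or ALT, refer the reader to the Medical Monitor discussion in the Section 4.7.6 note, so that any continuation follows one route.

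The cost is one clause and one cross-reference in Appendix 2. Design, sample size, data collection and analysis do not change.

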APPENDIX 3 RECIST 1.1 GUIDELINES

1 EVALUATION OF LESIONS

At baseline, tumor lesions/lymph nodes will be categorized measurable or non-measurable as follows:

1.1 Measurable

Tumor lesions: Must be accurately measured in at least one dimension (longest diameter in the plane of measurement is to be recorded) with a minimum size of:

1. 10 mm by CT scan (CT scan slice thickness no greater than 5 mm)
2. 10 mm caliper measurement by clinical exam (lesions which cannot be accurately measured with calipers should be recorded as non-measurable)
3. 20 mm by chest x-ray

Malignant lymph nodes: To be considered pathologically enlarged and measurable, a lymph node must be ≥ 15 mm in short axis when assessed by CT scan (CT scan slice thickness recommended to be no greater than 5 mm).

Lymph nodes merit special mention since they are normal anatomical structures which may be visible by imaging even if not involved by tumor. Pathological nodes which are defined as measurable and may be identified as target lesions must meet the criterion of a short axis of ≥ 15 mm by CT scan. Only the short axis of these nodes will contribute to the baseline sum. The short axis of the node is the diameter normally used by radiologists to judge if a node is involved by solid tumor. Nodal size is normally reported as two dimensions in the plane in which the image is obtained (for CT scan this is almost always the axial plane; for MRI the plane of acquisition may be axial, sagittal or coronal). The smaller of these measures is the short axis. For example, an abdominal node which is reported as being 20 mm x 30 mm has a short axis of 20 mm and qualifies as a malignant, measurable node. In this example, 20 mm should be recorded as the node measurement. All other pathological nodes (those with short axis ≥ 10 mm but < 15 mm) should be considered non-target lesions. Nodes that have a short axis < 10 mm are considered non-pathological and should not be recorded or followed.

